The use of the Mirena for the treatment of grade 1 endometrioid endometrial carcinoma has been less well studied, with only a few cases documented in the literature. Giannopoulos et al reported complete regression of a well-differentiated endometrial carcinoma after treatment with the LIUD[14]. Other case series, however, have had lower rates of success. Bahamontes et al treated two women with morbid obesity and G1EEC with the Mirena while awaiting gastroplasty for weight reduction. Both women had residual G1EEC in their hysterectomy specimens after 6 and 7 months, respectively[15,16]. In a case series of four women with G1EEC treated with LIUD, only one woman had complete regression at 6 months[16]. A larger study is necessary to clarify if the LIUD is effective in the treatment of grade 1 endometrioid endometrial carcinoma.

Given the success of oral progesterone for the treatment of both conditions, the LIUD is a rational option for patients with CAH and grade 1 endometrioid endometrial carcinoma. However, the existing literature is conflicting regarding the success of this treatment. Therefore, we propose a phase II trial to assess the efficacy of the LIUD for treatment of complex atypical hyperplasia or Grade 1 endometrioid carcinoma. Patients will receive this treatment for one year, as the median time to complete regression of G1 EEC during oral progesterone therapy is generally 12 weeks, with a range of 4 – 60 weeks[3].

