5.3 Pretreatment Evaluation

After signing the informed consent, the patients will follow one of two treatment plans depending on their initial biopsy diagnosis. All patients will undergo a urine pregnancy test (women of child bearing potential) and cervical cultures in clinic to rule out pregnancy and active cervical infection. Patients with G1 EEC will undergo clinical staging procedures including chest radiography and MRI of the abdomen and pelvis. This will be a routine MRI of the abdomen and pelvis with standard pulse sequences including dynamic gadolinium enhanced imaging of the uterus.

Women who are unable to undergo MRI due to morbid obesity or other contraindication will have a CT scan of the abdomen and pelvis and transvaginal ultrasound. For those patients who are unable to undergo CT due to morbid obesity, transvaginal ultrasound will be performed. Scans will be reviewed by the diagnostic radiology collaborator on the study. Women will be excluded if there is evidence of extrauterine spread of disease.

Both cohorts of patients (CAH and G1 EEC) will then undergo an exam under anesthesia (EUA) and a dilation and curettage (D&C) in the operating room to sample the entire endometrium. This specimen will be read by a certified gynecologic pathologist at our institution and report dictated in the electronic medical record. At the time of D&C, the LIUD will be placed. Women who have previously undergone D&C for this diagnosis will not be required to undergo a second D&C. The pathology specimen will be obtained for review and confirmation of diagnosis and for the correlative studies to be performed. The LIUD will then be placed in the clinic setting.

If patients with an initial diagnosis of CAH are upgraded to G1 EEC, they will be assessed for eligibility through inclusion criteria 1. If the patient does not meet inclusion criteria, they will be removed from the study. Otherwise, they will undergo chest radiography, and MRI of the abdomen and pelvis and/or CT of the abdomen and pelvis and/or transvaginal ultrasound as detailed above in the post-operative period. Women will remain on study if they have confirmed CAH and/or G1 EEC on the D&C specimen and have no evidence of extrauterine spread of disease. If a woman is excluded from the trial after LIUD is placed, the LIUD will be subsequently removed. Removal of the LIUD can be performed in the operating room if the patient proceeds with surgical treatment or in the clinic.

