5.4 Evaluation During Study

All subjects will be evaluated at one month (+/- 1 week) after LIUD placement to confirm the placement of the LIUD. This visit may be performed at MD Anderson or at the subject's local physician office, based on patient preference. Placement will be confirmed by speculum exam and, if necessary, using pelvic ultrasound.

Endometrial biopsy may be performed while the LIUD is left in situ. The endometrial biopsy will be performed with the Pipelle endometrial suction instrument (Cooper Surgical, Trumbull, CT). Each patient will have a follow-up endometrial biopsy every three months for one year (+/- 2 weeks). Endometrial evaluation every three months is the standard of care for patients with CAH or G1EEC undergoing conservative therapy. The pathology of the endometrial biopsies will be read by a certified gynecologic oncologist and report dictated in the electronic medical record.

The molecular profile of the endometrial lesion in the pre-treatment D&C specimen and 3-month post treatment biopsy will be determined. Using formalin-fixed, paraffin-embedded tissue, the mRNA expression profile will be determined by real time reverse transcriptase polymerase chain reaction for a panel of genes including PR, EIG121, IGF-I, IGF-IR, RALDH2, sFRP1, and sFRP4. The level of mRNA expression will be normalized by comparison to the expression of α -actin and 18S, two cellular housekeeping genes. See Appendix D for RT-PCR protocol. Protein expression

of PTEN and phosphorylated mTOR will be determined through the performance of immunohistochemistry on the formalin-fixed, paraffin-embedded endometrial biopsy specimens. See Appendix E for the immunohistochemistry protocol.

An evaluation of any complications related to the LIUD will be completed at each follow-up visit by study personnel. This assessment can be found in Appendix F. It includes concerns which are specific to the LIUD as well as typical side effects of systemic progesterone therapy. In addition, the patient will be given a diary to fill out at home during the first 3 months after LIUD placement. This diary is provided by Bayer and monitors vaginal bleeding after LIUD placement. See Appendix I for this diary.

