6.1.1.2 Three-Month Endometrial Biopsy

This sample will be collected in the clinic room using the Pipelle collection device. Adequate tissue amount will be determined by the clinician and research coordinator collecting the specimen. Upon collection, the specimen will be formalin-fixed and taken to the laboratory at room temperature.

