6.1.2 Handling of Sample

6.1.2.1 Dilation and Curettage and Three-Month Endometrial Biopsy

A hematoxylin and eosin slide will be prepared for the gynecologic pathologist to read and obtain diagnosis. The remainder of the tissue will be divided for PCR and IHC. RNA extraction will be performed on the tissue and the resultant RNA will be stored in the -80°C refrigerator until analysis.

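### Change at the 3-month biopsy may mix drug effect within the lesion with loss of the lesion, and section 7.5 takes no account of 3-month histology

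*Combined protocol and SAP*

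**What the plan says.** Objective 1.1.2, listed as primary, asks whether response can be predicted from the tumor's molecular profile or from the change in gene expression after therapy. Section 5.4 defines the material: "The molecular profile of the endometrial lesion in the pre-treatment D&C specimen and 3-month post treatment biopsy will be determined". The visit window is plus or minus two weeks.

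Section 2.2 gives the only regression time in the document: "the median time to complete regression of G1 EEC during oral progesterone therapy is generally 12 weeks", with a range of 4 to 60 weeks. It is cited to justify one year of LIUD treatment.

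For the 3-month sample, section 6.1.1.2 sets a condition on quantity only: "Adequate tissue amount will be determined by the clinician and research coordinator collecting the specimen". Section 6.1.2.1 adds: "A hematoxylin and eosin slide will be prepared for the gynecologic pathologist to read and obtain diagnosis". The remaining tissue is divided between PCR and IHC. Section 6.2.3 scores PTEN and phosphorylated mTOR by the percentage of endometrial glands in the specimen.

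Section 7.5 tests mean log change in each mRNA marker against zero with a paired t-test in all patients. It tests IHC change against response by chi-square. Neither analysis refers to the 3-month histology. Section 2.3 gives the paired mRNA data a second purpose, as pharmacodynamic evidence of an effect on the endometrium.

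**The concern.** A patient whose lesion has cleared by 3 months contributes a pair made of two different tissues: lesion at baseline, and treated endometrium without lesion at follow-up. Section 2.3 reports that IGF-IR rises stepwise from normal endometrium to G1 EEC, and that G1 EEC expresses the estrogen-induced genes highly. Loss of the lesion could therefore lower measured expression with no change inside lesion cells. Likewise, if lesional glands are replaced by normal ones, a percentage-of-glands score can change for that reason alone.

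Patients clear at 3 months are also likely to be among the 12-month responders. An association between change and response could then arise because the lesion had already gone, and be reported under 1.1.2 as prediction. That would matter to anyone planning to use 3-month change as a marker in patients whose histology is still uncertain.

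**Working it through.** **1. The plan's own figure.** Table 2 gives 93.39% power (SD 1) and 79.18% (SD 1.25) at n = 50. Power of the two-sided 5% paired t-test comes from the noncentral t distribution with n − 1 degrees of freedom and noncentrality (0.5/SD) × √n. All 14 cells reproduce to two decimals, with the stated SD used as the SD of the change.

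**2. Timing.** Three months is about 13 weeks, with a window of about 11 to 15. Take the 12-week median as applying to complete regressors and assume a distribution shape.
- Exponential: share clear by week w = 1 − 0.5^(w/12), giving 47% at week 11, 53% at week 13 and 58% at week 15.
- Lognormal, with spread set from the 4 to 60 week range: 43–45%, 55–56% and 63–67%.

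So about half would be clear at the visit, if the oral median carried over.

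**3. Number of patients.** With 65% complete response (the goal in 7.4, where the worked examples count complete remissions):
- half clear: 50 × 0.65 × 0.50 = 16.25, about 16 patients, leaving about 34 with lesion;
- a quarter clear: 50 × 0.65 × 0.25 = 8.1, about 8 patients, leaving about 42.

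**4. Effect on the pooled mRNA test.** Mean change = p × (shift from tissue change) + (1 − p) × (drug effect within lesion). With p = 0.325 and no effect within the lesion, a shift of 0.5/0.325 = 1.54 log units (e^1.54, about 4.7-fold) reproduces the planned mean change of 0.5. The table gives the probability that the paired t-test rejects when there is no effect within the lesion (20,000 simulated trials, n = 50, SD 1). The documents give no shift size, so these are assumptions.

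| Complete responders clear at 3 months | Shift 1.0 | Shift 1.5 |
|---|---|---|
| Half | 53% | 79% |
| A quarter | 18% | 31% |

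**5. Effect on a comparison with response.** Suppose 32 responders and 18 non-responders are compared by t-test on change, and clearance is the only source of difference. The result is significant at 5% in 33% (shift 1.0) to 57% (shift 1.5) of trials if half the responders are clear, and in 11% to 18% if a quarter are. Section 7.5 does not plan this test for mRNA; it illustrates what a claim under 1.1.2 would face.

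**6. Power with lesion-present pairs only.** For change against zero, by the formula in step 1:
- n = 34: 81% (SD 1), 62% (SD 1.25);
- n = 42: 89%, 72%.

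For a 0.5 difference between about 16 responders (32 − 16) and 18 non-responders, a two-sample t-test has 32 degrees of freedom and noncentrality (0.5/SD) × √(16 × 18/34), which is 1.46 or 1.16. Power is 29% (SD 1) or 20% (SD 1.25). The same formula with all 50 patients (32 against 18) gives 38% or 27%, so the pooled comparison is weak too.

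**The case against.** **The 12-week median may not apply.** It is for oral progesterone in G1 EEC. This trial uses an LIUD and also enrols CAH. The device data cited for G1 EEC contain no 3-month rate and vary: 7 of 11 clear at 6 months with a different device, 1 of 4 at 6 months with the LIUD, and two further women with residual disease at 6 and 7 months. This stands. A reader might infer that half of responders will have no lesion at 3 months; the documents do not support that. Clearance could also be faster than the device data suggest, because the baseline procedure is a "dilation and curettage (D&C) in the operating room to sample the entire endometrium".

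**Response is not the same as absence of lesion.** Section 7.3 counts partial responders, who still have CAH under 5.5, and complete response allows hyperplasia without atypia. This stands, and is why the counts above refer to complete responders and remain approximate.

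**Section 7.5 does not test mRNA change against response.** This is correct. The risk of false prediction lies in the planned IHC chi-square test and in any mRNA claim made under 1.1.2, not in the paired t-test itself.

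**The paired data have a pharmacodynamic purpose.** For that aim, change in treated endometrium is what counts and the mixing does little harm. However, the study cited in 2.3 for the 3-month time point was in patients without endometrial disease, so it does not address loss of a lesion.

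**Clearance at 3 months is not the endpoint.** Response is scored at one year, so it would be too strong to call the association circular. Early clearance is an early sign of response, and can explain part of an association.

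**Appendices D and E (RT-PCR and IHC methods) were not available to me** and may contain tissue-selection rules. If so, the gap narrows to the analysis in 7.5.

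**Conclusion.** The concern holds in a limited form. The 3-month sample is taken near the only regression time the protocol cites, lesion-free samples are foreseeable, and the text reviewed neither says how they are handled nor brings 3-month histology into 7.5. The pooled change is then a mixture, and an association of change with 12-month response may partly be early response.

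The size is uncertain. About 16 of 50 patients would be lesion-free if the oral median applied and 65% responded completely; about 8 if a quarter of complete responders were clear. The rejection rates in the working also depend on assumed shifts.

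A reader might infer that objective 1.1.2 as a whole cannot be answered. The documents do not support that: the baseline-profile half is little affected, as is the pharmacodynamic aim. What is exposed is a claim that change predicts response. This should be changed before analysis; it does not threaten the design.

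**What to change.** In section 7.5:
- Classify each 3-month sample as lesion-present or lesion-absent from the H&E slide already read, and state how lesion-absent samples are handled.
- Keep the pooled paired t-test, described as pharmacodynamic evidence, and also report mRNA and IHC change separately in the two groups.
- Report the association of change with 12-month response (IHC as planned; mRNA if a claim is made under 1.1.2) both overall and within lesion-present patients. Label the latter a 3-month landmark analysis. It answers a narrower question: whether change predicts later response in patients not yet clear.
- Claim prediction only from the baseline profile or the landmark result. Describe an association driven by lesion-absent samples as early response.

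The cost is a few extra tabulations, with no new tissue, visits or readings. The downside is a small landmark group. With about 34 pairs, power for change against zero remains moderate, but the responder comparison is badly underpowered (step 6 of the working). It should be labelled exploratory, and a null result there should not be read as evidence of no association. The landmark analysis should sit beside the pooled analysis. Replacing the pooled analysis would lose pairs that serve the pharmacodynamic aim.

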5.5 Criterion for Response

Response is defined as follows:

Complete response is defined as no endometrial abnormality or the presence of endometrial hyperplasia without cytologic atypia at the one year time point.

Partial response is defined as the presence of complex endometrial hyperplasia with cytologic atypia in patients with an initial diagnosis of grade 1 endometrial cancer, at the one year time point.

Stable disease is defined as no change in diagnosis at the one year time point.

Progressive disease is the presence of grade 2 cancer or above in patients with an initial diagnosis of grade 1 cancer OR presence of grade 1 cancer or above in patients with an initial diagnosis of complex atypical hyperplasia at any time point.

Patients with stable disease or progressive disease will be categorized as non-responders for the purposes of molecular analysis.

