5.6 Criteria for Removal From Study

At the one year time point the patient will complete the study. If progression of disease is noted at any time, the patient will be taken off study and at the physician's discretion, the LIUD may be removed and the patient will be treated with either definitive surgical therapy or an alternative progesterone agent. In the case of G1 EEC, progression will be defined as the presence of grade 2 endometrioid cancer or worse on the endometrial biopsy. In the case of CAH, progression will be defined as G1 EEC or worse on the endometrial biopsy. The patient will also be removed from the study and offered alternative therapies if unacceptable toxicity or complications occur due to the LIUD.

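### Section 5.5 scores partial response and progression against an undefined 'initial diagnosis', so women reclassified at the pre-treatment D&C can be misclassified on the primary endpoint

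*Combined protocol and SAP*

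**What the plan says.** - **Section 5.5.** Progressive disease includes "presence of grade 1 cancer or above in patients with an initial diagnosis of complex atypical hyperplasia at any time point". Partial response is CAH "in patients with an initial diagnosis of grade 1 endometrial cancer, at the one year time point". Complete response is judged at one year and needs no baseline. Stable disease is an unchanged diagnosis, without saying unchanged from what. Stable and progressive disease are both non-response in the molecular analysis. 'Initial diagnosis' is not defined.
- **Section 5.3.** After consent, "the patients will follow one of two treatment plans depending on their initial biopsy diagnosis". Then: "If patients with an initial diagnosis of CAH are upgraded to G1 EEC, they will be assessed for eligibility through inclusion criteria 1". Those who fail that check leave; otherwise "Women will remain on study if they have confirmed CAH and/or G1 EEC on the D&C specimen", provided there is no extrauterine spread. "At the time of D&C, the LIUD will be placed". Where a D&C was done earlier, its specimen is obtained for review and the LIUD is placed in clinic.
- **Section 5.6.** "If progression of disease is noted at any time, the patient will be taken off study". "In the case of CAH, progression will be defined as G1 EEC or worse on the endometrial biopsy".
- **Sections 7.1 to 7.4.** Evaluable means completing 12 months (7.1). The primary outcome is complete or partial response at one year (7.3), but the futility boundaries (7.2) and the worked credible intervals (7.4) count complete remissions.

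**The concern.** A response category needs a fixed starting point. Section 5.5 takes its starting point from a phrase that 5.3 uses for a label the D&C can overturn. For a woman whose D&C agrees with her biopsy this does not matter. For a woman reclassified at the D&C, the endpoint can record the difference between two pre-treatment specimens as an effect, or a failure, of the LIUD.

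Two analyses are exposed: the primary response rate, and the responder label used to ask whether molecular profile predicts response (objective 1.1.2). Section 8.0 makes the study chair the final arbiter of response. With two readings open, the choice between them could be made patient by patient, after the outcome is known, in a single-arm trial.

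**Working it through.** **1. What 'initial' means.** Section 5.3 speaks of the initial biopsy diagnosis, then of an initial diagnosis of CAH that the D&C may upgrade. A diagnosis that the D&C can upgrade is not the D&C diagnosis. Section 5.5 uses the same words with no other definition.

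**2. The pathways side by side.**

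| Biopsy → D&C → follow-up | Biopsy label as baseline | D&C diagnosis as baseline |
|---|---|---|
| A. CAH → G1 EEC → G1 EEC, unchanged | Progression, at the D&C or at the first follow-up biopsy | Stable |
| B. CAH → G1 EEC → CAH at one year | Progression if the D&C counts; otherwise stable; never partial response | Partial response |
| C. CAH → G1 EEC → no atypia at one year | Meets complete response and, if the D&C counts, progression; no precedence rule | Complete response |
| D. G1 EEC → CAH → CAH at one year | Partial response | Stable |
| E. G1 EEC → CAH → G1 EEC at one year | Stable | Progression |

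A and E are non-response either way. A still matters: on the biopsy label, 5.6 takes her off study at the first unchanged biopsy, so a later response cannot be observed. B, C and D can change the success count.

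**3. The plan's own figures.** With prior Beta(1.3, 0.7), the posterior after x successes in n is Beta(1.3 + x, 0.7 + n − x). The verbal rule in 7.2 stops when Pr(rate ≥ 65%) < 0.05, here checked after every patient from n = 20. All 18 listed boundaries reproduce. The exact probability of stopping at a true 65% is 13.2% (plan: 13.3%); at a true 50% it is 79.9% (plan: 79.3%).

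**4. Size per patient.** 1/50 = 2 points at full size; 1/20 = 5 points at the first futility look.

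**5. Illustration, upgrades.** Let c be the share with CAH on biopsy and u the share of those upgraded and retained. Neither is in the documents. Affected patients number 50cu. If all are failures, so that progression overrides any later response, the observed rate at a true 65% is 0.65 × (1 − cu).

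| c | u | Patients of 50 | Observed rate | P(stop early) |
|---|---|---|---|---|
| 0.6 | 0 | 0 | 65.0% | 13.2% |
| 0.6 | 0.10 | 3 | 0.65 × 0.94 = 61.1% | 27.0% |
| 0.6 | 0.20 | 6 | 0.65 × 0.88 = 57.2% | 45.8% |

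Over c from 0.4 to 0.8 and u from 0.10 to 0.42, this gives 2 to 16.8 patients and P(stop) from 21.7% to 96.1%. The top of that range borrows the 42% in section 2.1, which was found at hysterectomy. It is a ceiling, not an estimate.

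The result depends on the accounting:
- If women removed as progressors have not completed 12 months, they may leave the evaluable denominator. The rate then describes only women who were not upgraded.
- If they stay on study, complete response at one year overrides progression, and only complete remissions are counted (7.2, 7.4), the loss is zero.

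**6. Illustration, downgrades (pathway D, and only under 7.3).** Let f be the share of all patients downgraded from G1 EEC to CAH at the D&C. Take a true complete response rate of 50%, with the other downgraded women keeping CAH. The observed rate is 0.50 + f × 0.50.
- 2 of 50 downgraded: 0.50 + 0.04 × 0.50 = 52%; P(stop) falls from 79.9% to 71.7%.
- 6 of 50 downgraded: 0.50 + 0.12 × 0.50 = 56%; P(stop) falls to 52.0%.

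**The case against.** The best defence is that the protocol already intends a D&C baseline. Section 5.3 keeps upgraded women while 5.6 removes progressors, and these agree only if a D&C upgrade is not progression. Section 5.6 drops 'initial' and judges progression on the endometrial biopsy. Section 5.4 describes that as the three-monthly Pipelle sample, and 4.2.2 lists it separately from the D&C specimen. Section 5.3 obtains the specimen to confirm the diagnosis.

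This makes a D&C baseline plausible, so a reader who infers that upgraded women certainly are progressors at entry goes too far. But the baseline is nowhere stated. Nor does limiting progression to follow-up biopsies settle it: if 'the case of CAH' in 5.6 follows the biopsy label, unchanged G1 EEC at three months is still progression.

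Three other inferences also fail:
- That downgraded women are partial responders before treatment. Partial response exists only at one year; the fault is that unchanged CAH then qualifies.
- That the loss is about 3 to 14 points (25 × 0.10 × 0.65 = 1.6 patients to 25 × 0.42 × 0.65 = 6.8 patients, of 50). This assumes that half enter with CAH, that progression overrides complete response, and, at the upper end, that every cancer seen at hysterectomy is found at D&C in a woman who still qualifies.
- That the protocol expects such patients to be common. Section 2.1 reports diagnostic overlap and 38% agreement on CAH, so reclassification is foreseeable, but no D&C rate is given.

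**Conclusion.** The point stands as an undefined baseline that conflicts with 5.3 when read in the protocol's own terms. It can misclassify the primary endpoint in both directions, and the molecular responder label with it.

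The size is not known from the documents. It is 2 points of 50 per misclassified patient. In the illustration, three upgraded women counted as failures roughly double the chance of a futility stop at a true 65%, from 13.2% to 27.0%. That rests on assumed reclassification rates and on progression overriding later response. The downgrade effect arises only if partial response counts as success, as 7.3 says and 7.2 and 7.4 do not. The change should be made, because the definition is cheap to settle before outcomes are read and hard to defend afterwards.

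**What to change.** - In 5.5, replace 'initial diagnosis' with a baseline diagnosis, defined as the D&C-confirmed diagnosis, using the earlier D&C specimen where no second D&C is done. Refer stable disease to the same baseline.
- For the endpoint, score progression only on biopsies taken after LIUD placement.
- State whether progression at any time overrides complete or partial response at one year, and whether women removed as progressors count as failures or are non-evaluable.
- Use the same baseline for responder status in the molecular analysis, whose pre-treatment tissue is already the D&C specimen, and for the 'original disease state' in the recurrence definition of 7.5.
- On the biopsy-label reading, 5.3, 5.5 and 5.6 contradict each other on who stays on study. The protocol team must reconcile them; that is not a statistical choice.

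Taking the worse of biopsy and D&C as baseline would not do: it repairs pathways A to C but still scores D as a partial response.

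**Cost.** A few sentences and no new data, since D&C pathology is already obtained. A woman with G1 EEC on biopsy but CAH on D&C can no longer be a partial response, so the reported rate may be slightly less favourable. Pathway E moves from stable to progressive, which leaves the one-year success count unchanged but bears on the removal wording to be reconciled.
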